6.6. Efficacy

6.6.1. Primary Efficacy Analysis

There is no primary efficacy analysis. The primary objective of the study is to evaluate safety and tolerability of SB-121. All safety assessments are presented in the applicable safety sections.

6.6.2. Secondary Analysis

[REDACTED]. These measures are: Clinical Global Impressions Severity and Improvement Subscales, Vineland Adaptive Behavior Scales (3rd edition), Aberrant Behavior Checklist, Woodcock Johnson Test (3rd Edition), Repeatable Battery for Assessment of Neuropsychological Status (RBANS), Test of Attentional Performance for Children (KiTap), Neurophysiology Measures including EEG resting state, auditory habituation, and chirp modulated sweep auditory evoked response, and Eye Tracking and Pupillometry measures.

The number and percentage of subjects with incidence of presence of Sephadex® microspheres in the stool and incidence of symptomatic bacteremia with positive *L. reuteri* identification will be summarized by treatment group by visit and listed based on the ITT population.

The stool and blood samples will be used for the evaluations of potential biomarkers of inflammation (fecal calprotectin and lactoferrin and blood hs-CRP and tumor necrosis factor- α). In accordance with the baseline value definition in Section 5.1.2, the absolute change from baseline will be derived as follows:

Absolute change (unit) = (post-baseline value – baseline value)

The following will be summarized by treatment group for the ITT population:

- Observed values and percentage change from baseline at each assessed visit, including comparison of baseline to end of Treatment Period 1 and baseline to end of Treatment Period 2, for each biomarker parameter using summary statistics for continuous variables;

A listing of all biomarkers data including derived change from baseline will be provided for the Safety population.

Plasma oxytocin and vasopressin levels will also be analyzed. In accordance with the baseline value definition in Section 5.1.2, the absolute change from baseline will be derived as follows:

Absolute change (unit) = (post-baseline value – baseline value)

The following will be summarized by treatment group for the ITT population:

- Observed values and percentage change from baseline at each assessed visit, including comparison of baseline to end of Treatment Period 1 and baseline to end of Treatment Period 2, for each parameter using summary statistics for continuous variables;

A listing of all plasma oxytocin and vasopressin data including derived change from baseline will be provided for the ITT population.

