6.2.1.1 Endpoints

Endpoints in this study are as follows:

Primary endpoints:

- Incidence and severity of treatment-emergent AEs (TEAEs), serious AEs (SAEs), AESIs, and AEs leading to discontinuation from the study
- Incidence of presence of Sephadex® microspheres in the stool
- Incidence of symptomatic bacteremia with positive *L. reuteri* identification

Secondary endpoints:

Change from baseline in:

- Clinical Global Impressions Severity and Improvement Subscales
- Vineland Adaptive Behavior Scales (3rd edition)
- Aberrant Behavior Checklist
- Woodcock Johnson Test (3rd Edition)
- Repeatable Battery for Assessment of Neuropsychological Status
- Test of Attentional Performance for Children (KiTap)
- Neurophysiology Measures including EEG resting state, auditory habituation, and chirp modulated sweep auditory evoked response
- Eye Tracking
- Biomarkers in stool and blood samples: Plasma oxytocin, plasma vasopressin, serum hs-CRP, tumor necrosis factor- α , and stool biomarkers.

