 - Sample 2 should be taken approximately 7 days into the wash-out period after the first treatment period of the study and before the second treatment period
 - Sample 3 should be taken no sooner than 21 days or later than 28 days into the second treatment period of the study (prior to the completion of the second treatment period)
 - Sample 4 should be taken approximately 7 days after the completion of the second treatment period of the study

Subjects will be advised to contact the study site immediately in the event of symptoms consistent with bacteremia (e.g., fever, chills, diaphoresis) to obtain appropriate medical care as indicated. In the event that subjects develop symptoms consistent with bacteremia, 2 blood samples will be collected, when feasible for blood cultures, and microbial identification.

Follow-up visits will be conducted on Day 28 of treatment period 1, Day 1 of treatment period 2 and Day 28 of treatment period 2 as per the Schedule of Events.

Details of AEs occurring throughout the study will be captured at each visit, additionally AEs of special interest will be captured in the Patient Diary. Weekly telephone calls will be conducted by the study team between in person visits during each treatment period. These calls will record and evaluate adverse events and will also determine IP compliance. In the case of adverse events identified during a phone call, the study team may determine that an unscheduled in-person study visit and/or lab tests may be required. Gastrointestinal events (nausea, vomiting, diarrhea, constipation, abdominal distention, abdominal pain/cramps, and flatulence) and systemic events (fever, chills, diaphoresis) occurring at any time during the study and within 2 weeks after the last dose of IP will be considered AEs of special interest (AESIs), and will be solicited.

The investigational product will be provided to subjects in 2 bottles, the contents of which will be combined, allowed to sit for a period of 15-45 minutes at room temperature, then combined with a predefined drink for consumption. See the Daily Medication Instructions for additional details.

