10.2.6.2 Clinical Laboratory Safety Assessments

10.2.6.2.1 Clinical Laboratory Tests to be Performed

Samples for the following laboratory tests will be collected at the timepoints specified in the Schedule of Events (Section 2.2):

Hematology: hemoglobin, hematocrit, red blood cell (RBC) count, mean corpuscular hemoglobin, mean corpuscular volume, mean corpuscular hemoglobin concentration, platelet count, white blood cell count including differential (to also include absolute neutrophil, lymphocyte and eosinophil counts)

Serum Chemistry: albumin, total and direct bilirubin, total protein, calcium, alkaline phosphatase, alanine aminotransferase, aspartate aminotransferase, blood urea nitrogen, creatinine, glucose, sodium, potassium, chloride, bicarbonate, lactate dehydrogenase, uric acid, highly sensitive C-reactive protein

Urinalysis pH, specific gravity, blood, glucose, protein, ketones
(dipstick): (microscopic evaluation will be conducted in case of abnormal findings)

Urine Pregnancy for women of childbearing potential only
Test:

Urine Drug Screen amphetamines, barbiturates, benzodiazepines, cocaine, opiates, and
(Screening only): phencyclidine

Subjects are not required to be fasted at the time of sampling for clinical laboratory tests.

Blood samples will be up to 20 mL in volume. The total amount of blood to be drawn will be a maximum of 80 mL per subject.

The normal ranges of values for the clinical laboratory assessments in this study will be provided by the responsible laboratory. They will be regarded as the reference ranges on which decisions will be made.

[figure not shown]
All laboratory values out of the reference range, are not necessarily clinically relevant. The investigator must evaluate the out-of-range values and record this assessment of the clinical relevance in the appropriate eCRF. All clinical laboratory values that, in the investigator's opinion, show clinically relevant changes must be reported as AEs up to 14 days after the second study period.

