10.2.6.2.3 Microbe Identification in for Suspected Bacteremia

In the event that a subject develops symptoms consistent with bacteremia (e.g., fever, chills, diaphoresis), attempts will be made to collect appropriate blood samples for microbial identification using culture bottles; subjects should attend clinic at their earliest convenience to provide a blood sample. Details for the correct handling of the samples will be provided in the laboratory manual.

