5.1.4. Visit Windows

All data will be analyzed using nominal study visit as defined in the Study Schedule per the protocol and eCRF. No visit windows will be applied for summary and analysis.

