6.1. General Principles

For the purposes of this SAP, all data processing, summarization and analyses will be performed using [REDACTED] Drug Development's SAS Environment / Version 9.4 (or later) of the SAS® statistical software package. When summarizing data by treatment group, results will be combined across the study periods. For example, the data from subjects who received SB-121 in Treatment Period 1 will be combined with the data from subjects who received SB-121 in Treatment Period 2. An additional analysis will be done for change of certain parameters to end of Treatment Period 1 and end of Treatment Period 2, respectively, utilizing as Baseline values the last observation prior to dosing in Treatment Period 1. This will be done for each treatment group. These parameters may include fecal calprotectin and lactoferrin, serum hs-CRP and tumor necrosis factor- α , and plasma oxytocin and vasopressin levels.

The default summary statistics for quantitative variables will be the number of observations (n), mean, standard deviation (SD), median, minimum (min) and maximum (max), for those subjects with data.

For qualitative variables, the number (n) and percentage (%) of subjects with non-missing data per category will be the default summary presentation, and where appropriate and present, the number of missing values as a “Missing” category. Number of subjects in the analysis population will be used as denominator for percentages calculation, unless stated otherwise in TFLs mock shell(s).

For the TFLs, the laboratory results will be summarized or presented in International System of Units (SI) units.

Specifications for table, figures and data listing formats can be found in the TFL shells specifications for this study. Please refer to “2. General Format Guidelines” section within TFL shells for more details on presentation of results.

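### The primary endpoint of symptomatic L. reuteri bacteremia is summarised by nominal visit although cultures are symptom-triggered, so the table gives no incidence per treatment and does not separate culture-negative from never-cultured subjects

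*SAP*

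**What the plan says.** - Protocol 6.2.1.1 lists as a primary endpoint: "Incidence of symptomatic bacteremia with positive" L. reuteri identification. SAP 2.7 lists the same item as a safety variable.
- Protocol 7.1, on subjects with symptoms that suggest bacteremia (fever, chills and diaphoresis are the examples): "2 blood samples will be collected, when feasible for blood cultures, and microbial identification". Protocol 10.2.6.2.3 promises attempts at collection and adds that "subjects should attend clinic at their earliest convenience to provide a blood sample". The Schedule of Events (Protocol 2.2) has no blood-culture row.
- SAP 6.6.2 covers stool microspheres and bacteremia in one sentence. Bacteremia with positive L. reuteri "identification will be summarized by treatment group by visit and listed based on the ITT population". Protocol 13.1.4.2 asks for a summary and a listing of the same two items and does not mention visits.
- SAP 5.1.4: "All data will be analyzed using nominal study visit as defined in the Study Schedule per the protocol and eCRF". It adds: "No visit windows will be applied for summary and analysis".
- SAP 6.1: "Number of subjects in the analysis population will be used as denominator for percentages calculation". The sentence goes on to allow exceptions in the table shells. The same paragraph allows a category for missing values where appropriate and present.
- SAP 6.7.2 assigns each TEAE to a treatment by when it occurs, from the first dose of one period to the first dose of the next or to the end of study. The rule is written for TEAEs only.

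**The concern.** A by-visit summary suits stool samples, which have planned times. A bacteremia work-up starts when symptoms appear, usually between planned contacts, and may not take place at all. Two problems follow.

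1. **Placement.** No stated rule assigns an off-schedule culture to a visit or to a treatment period. Even if every culture had a visit label, counts by visit are not the proportion of subjects with at least one case on each treatment, which is what the endpoint asks for.
2. **Meaning of zero.** A case needs a positive identification. A symptomatic subject without a culture can never enter the numerator but stays in the default denominator. The summary cannot show whether a zero means tested and negative or not tested.

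This is the first study of SB-121 in humans, the product contains live bacteria, and Protocol 12 provides for no data safety monitoring board. The primary safety result should show how many symptomatic subjects were actually examined for the organism.

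**Working it through.** The documents give no event rate, no expected number of symptomatic subjects and no precision target, and the sample size is not based on statistical assumptions. There is no planned figure to reproduce. The check sets the rules side by side and then illustrates the size.

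**Step 1: where does a culture land?** Trigger: symptoms (Protocol 7.1, 10.2.6.2.3). Timing: an attendance outside the planned visits. Planned culture visits: none (Protocol 2.2). Analysis time point: nominal visit, no windows (SAP 5.1.4). Rule mapping an off-schedule culture to a visit: none stated. Rule attributing it to a treatment: none stated, because the rule in SAP 6.7.2 covers TEAEs only.

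**Step 2: how does an uncultured symptomatic subject count?** Numerator: no, because there is no positive identification. Denominator: yes by default (SAP 6.1). Separate row: not specified. SAP 6.5 does prescribe a missing category for compliance, but SAP 6.6.2 prescribes none here.

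**Step 3: size.** Assume that all 16 planned subjects receive SB-121 in one of the two periods and that no culture is positive.

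- Result over all subjects: 0/16 = 0%.
- Exact two-sided 95% upper limit: 1 − 0.025^(1/16) = 0.206, or 20.6%. This holds whether all or none of the symptomatic subjects were cultured.
- Let f be the number symptomatic and c the number of those cultured. The data are then compatible with an incidence from 0 to (f − c)/16:

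| Symptomatic, not cultured (f − c) | Highest compatible incidence |
|---|---|
| 1 | 1/16 = 6.25% |
| 2 | 2/16 = 12.5% |
| 3 | 3/16 = 18.75% |
| 4 | 4/16 = 25% |

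- One detected case should read 1/16 = 6.25% (exact 95% interval 0.2% to 30.2%). If its culture carries no nominal visit, every by-visit cell reads zero.

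**Step 4: population.** SAP 2.7 makes this a safety variable. SAP 4.3 uses the Safety population, by treatment received, for all safety analyses. SAP 6.6.2 uses ITT, which SAP 4.2 analyses by randomized treatment. The sections disagree.

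**The case against.** The strongest reply is that nothing is lost from the report. SAP 6.6.2 itself requires a listing. Bacteremia would be an adverse event, tabulated and attributed under SAP 6.7.2. Fever, chills and diaphoresis are solicited events of special interest with their own table and listing. With at most 16 subjects, a reader could compare the listings by hand. The eCRF may carry an unscheduled visit, and the table shells, which are not among the documents, may set another denominator or add a missing row. A subject without an identification is also a non-case by definition.

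Most of this stands, and it limits the point. It does not remove it. The event-of-special-interest tables show symptoms, not culture status, so no summary described in the SAP separates cultured and negative from never cultured. If non-detection is a non-case by definition, the number of subjects examined becomes more important.

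A reader might infer three stronger things that the documents do not support:

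- **That a positive case would go unreported.** It would be missing at most from this endpoint's summary table.
- **That the SAP imputes uncultured subjects as negative.** It has no such rule, and SAP 5.2.2 says that missing laboratory data are in general not imputed. The effect comes from the default denominator.
- **That the blood limit rules out cultures.** Protocol 10.2.6.2.1 says "The total amount of blood to be drawn will be a maximum of 80 mL per subject", but its per-sample volume is a ceiling, and the section does not say that symptom-triggered cultures count towards the limit.

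**Conclusion.** The concern holds as a mismatch between a stated summary and the way the endpoint arises. Followed as written, SAP 6.6.2 yields no incidence of bacteremia per treatment, may have no cell for an unscheduled positive, and lets a zero stand without showing how many symptomatic subjects were tested.

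The 20.6% limit belongs to any 0/16 and does not measure the defect. What measures it is the 6.25% to 25% upper end of the compatible range for 1 to 4 uncultured symptomatic subjects. Those counts are assumptions, since the documents give none. The range also assumes 16 treated subjects and that a negative culture is a true negative. If every symptomatic subject is cultured, the ambiguity about zero disappears, but the by-visit problem remains. The placement problem and the default denominator depend on the eCRF and the table shells not already providing otherwise. This warrants a change to the SAP; the trial design is not affected.

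**What to change.** In SAP 6.6.2, separate bacteremia from the stool sentence and drop the by-visit summary for it, in line with Protocol 13.1.4.2. Then:

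1. Report, per treatment, the number and percentage of subjects with at least one case. Include unscheduled cultures, and attribute by date of symptom onset using the TEAE intervals of SAP 6.7.2.
2. Show four counts per treatment: subjects with fever, chills or diaphoresis; subjects cultured; subjects positive for L. reuteri; and subjects symptomatic but not cultured, labelled not determined.
3. Reconcile the ITT population in SAP 6.6.2 with SAP 2.7 and 4.3, and state whether treatment is as randomized or as received.
4. Keep the listing.

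The cost is a few lines of SAP text and one small table. No extra subjects or visits are needed, and the culture procedure is unchanged. The downside is that the result may look less clean if cultures were missed.

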6.7. Safety

6.7.1. Extent of Exposure

Duration of exposure will be defined in days for each Treatment Period as:

Exposure (days) = [date of last dose in a Treatment Period– date of first dose in a Treatment Period] + 1 – off-treatment days

Duration of exposure will be summarized for the Safety population by treatment group using descriptive statistics.

A listing of overall treatment exposure data, including the first and last dates of treatment will be presented together with compliance for the Safety population.

6.7.2. Adverse Events

All AEs recorded on the eCRF will be coded using the MedDRA dictionary [version 24.0] and classified as either pre-treatment AEs or treatment-emergent AEs (TEAEs) as follows:

- Pre-treatment AEs are events that start prior to the start of Treatment Period 1.
- TEAEs are either events with start date after the start of the Treatment Period 1 (during or after the first dose of IP), or events with start date prior to the start of the Treatment Period whose severity worsens on or after the start of the Treatment Period (during or after the first dose of IP). A TEAE occurring on or after the first dose of treatment in Treatment Period 1 up until the first dose of treatment in Treatment Period 2 will be assigned to the treatment group received in Treatment Period 1. A TEAE occurring on or after the first dose of treatment in Treatment Period 2 up until the end of study will be assigned to the treatment group received in Treatment Period 2.

- Treatment-Emergent Serious AEs (TESAEs) will be defined as TEAEs regarded by the investigator as Serious = “Yes”.
- The relationship between a TEAE and SB-121 is assessed as definitely, probably, possibly, unlikely, or not related. A treatment-related TEAE will be defined as a TEAE considered by the investigator as definitely, probably, or possibly related to treatment or with unknown / missing relationship to treatment.
- Assessment of AE severity / intensity will be based on the National Cancer Institute-Common Terminology Criteria for AEs (NCI-CTCAE², version 5.0). If an NCI-CTCAE scale is not available for a given AE, the following definitions will be used:
 - Grade 1 (mild) • asymptomatic or mild symptoms; clinical or diagnostic observations only; intervention not indicated.
 - Grade 2 (moderate) • minimal, local or noninvasive intervention indicated; limiting age appropriate instrumental activities of daily living
 - Grade 3 (severe) • medically significant but not immediately life-threatening; hospitalization or prolongation of hospitalization indicated; disabling; limiting self-care activities of daily living
 - Grade 4 (life-threatening) • Life-threatening consequences; urgent intervention indicated
 - Grade 5 • Death related to AE

In addition to the aforementioned AE types, TEAEs of special interest will be identified as collected in the eCRF.

Adverse events will be summarized by descriptive summary statistics for categorical variables for the Safety population by treatment group as follows:

- An overview of TEAEs including the number and percentage of subjects with at least one TEAE type.
 - Any TEAE
 - TEAEs of Special Interest
 - Leading to discontinuation of study treatment
 - Leading to death
 - Grade 1 severity (mild)
 - Grade 2 severity (moderate)
 - Grade 3 severity (severe)
 - Grade 4 severity (life-threatening)

- Grade 5 severity (death)
- Any study treatment related TEAE
 - Leading to discontinuation of study treatment
 - Leading to death
- Any serious TEAE
 - Leading to discontinuation of study treatment
 - Leading to death
- Any serious study treatment related TEAE
 - Leading to discontinuation of study treatment
 - Leading to death
- The number and percentage of subjects reporting each TEAE and the count of number of events will be summarized by SOC and PT for the following types of TEAEs:
 - TEAEs of Special Interest
 - TEAEs Leading to Interruption of Study Treatment
 - TEAEs Leading to Discontinuation of Study Treatment
 - TEAEs Leading to Death
 - TEAEs by Maximum Severity
 - TEAEs that are Related to Study Treatment
 - Serious TEAEs
 - Serious TEAEs that are Related to Study Treatment

In the above summaries, subjects with more than one TEAE within a particular SOC are counted only once for that SOC. Similarly, subjects with more than one TEAE within a particular PT are counted only once for that PT.

For summaries by maximum severity, subjects with multiple TEAEs within a particular SOC or PT will be counted under the category of their most severe TEAE within that SOC or PT. TEAEs with missing severity will be included in the counts of the 'Number of Subjects with at least one TEAE', 'System Organ Class' and 'Preferred Term' rows of the summary but they will not be included in the counts by severity.

Summaries by SOCs and PTs will be sorted by SOCs and PTs within SOC by descending order of total incidence in the active treatment group. Where preferred terms tie PTs will be sorted alphabetically.

No statistical comparisons of AEs between treatment groups will be performed.

All AE data will be listed and Pre-treatment AEs and TEAEs will be presented together. Treatment-emergence status will be flagged in the listing. The listing will present the relative start and stop day of the AE calculated relative to the first dose of treatment in the Treatment Period when the AE started and will be presented for those subjects who received at least one dose of treatment. Only original dates will be presented in the listing even though the relative day may be based on an imputed date.

In addition, the following listings will be presented:

- Listing of Deaths
- Listing of Serious TEAEs
- Listing of AEs Leading to Interruption of Study Treatment
- Listing of AEs Leading to Discontinuation of Study Treatment
- Listing of AEs of Special Interest

